- 2) Since the patients for the second cycle are randomized to receive either neuronavigated or standard TMS, we can justify a second cycle of standard TMS by statistics from [name] clinics which are in agreement with application guidelines for the use of TMS (Rossi et al., 2009). As for [name] past experience is concerned, of the 139 patients that received 9 weeks of TMS, 60 responded at the 4 week point and 89 responded at the 8 week point. Of the 79 that did not respond at the 4 week measurement, 42 (more than 50%) responded at the week 8 point. Response is defined here as a 50% or greater reduction in starting Ham D score. As such, while the advantage of the second round of TMS is clear for the patients who receive neuronavigated TMS, even for the patients who receive the second round of standard TMS the above facts demonstrate the advantages of prolonged (4-8 week) treatment by TMS in the form of a 50% favorable outcome in that group of patients.

In addition to resting state functional connectivity, we will also assess glutamate (Glu) concentrations and resting-state cerebral blood flow/volume (rsCBF/rsCBV) in DLPFC and cortical midline structures (CMS) using Magnetic Resonance Spectroscopy (MRS) and Arterial Spin Labelling (ASL), respectively. CMS refer to brain structures situated near the medial wall of the brain and is mainly comprised of the ventral medial prefrontal cortex, dorsal medial prefrontal cortex, anterior cingulate cortex (the supragenual part in particular) and posterior cingulate cortex. Regional increases in Glu release increase the metabolic rate of post-synaptic neurons (28), and surrounding astrocytes (29), leading to regional BOLD signal increases (30). Glu concentrations may therefore be linked to overall functional connectivity patterns (31-34). In particular, Glu levels in left DLPFC in MDD provide an index of local metabolic activity, and abnormalities can be reversed in a dose-dependent manner by rTMS (35). These effects are present not only close to the stimulation site (left DLPFC), but also in remote (right DLPFC, left cingulate cortex) brain regions.

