Depressed Adults prescribed for the first time to standard TMS

Number of completers required to accomplish study aims

60

Projected number of subjects who will be enrolled to obtain required number of completers

70

Age range of subject population

18-60

Sample #2

Specify subject population

Depressed Adults non-responders to standard TMS

Number of completers required to accomplish study aims

30

Projected number of subjects who will be enrolled to obtain required number of completers

35

Age range of subject population

18-60

Gender, Racial and Ethnic Breakdown

Given the gender difference in the prevalence of major depression, it is expected that approximately 2/3 of the sample will be female. Expected ethnic breakdown is: 80% Caucasian, 10% African-American, 10% Hispanic or other ethnic group.

Description of subject population

All patients will be adults aged 18-60 who are to receive targeted rTMS for their depressive symptoms.

After passing all screening criteria, participants may still have their participation in the study ended if they do not comply with study procedures, if there is a change in their medical status, or if an adverse event has occurred.

Recruitment Procedures

Describe settings where recruitment will occur

Patients will be referred from private psychiatric facilities run by [name], and will be selected from those already participating in an approved clinical study of rTMS for treatment resistant depression (WIRB protocol #20141643 entitled: “Cognitive Changes During Treatment with TMS for Major Depression”, see attachment).

How and by whom will subjects be approached and/or recruited?

[name] will tell potential participants about the current study, using the consent form cover sheet and flyers for patients and doctors to describe the types of procedures involved. Potential participants interested in learning more will receive [name] contact information from [name] to call and make an appointment at NYSPI for a visit with her and Drs. [name] and [name]. (Please find the Screening Phone call Script attached). Screening protocol from [name]’s IRB # 6669R titled “Evaluation of Potential Participants for Depression Evaluation Service (DES) Research” will also be used.

How will the study be advertised/publicized?

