3. Duration of the index episode of at least 2 weeks. Psychiatric History
4. MDD symptoms, defined as a total HDRS-17 score ≥ 18 despite treatment with an adequate trial of a serotonin reuptake inhibitor (SRI). An adequate SRI trial is defined as treatment for at least 6-8 weeks on the SRI, that meets the maximum recommended dosage level for MDD (fluoxetine 40-60 mg/d, sertraline 100-200 mg/d, paroxetine 40-60 mg/d, fluvoxamine 200-300 mg/d, citalopram 40-60 mg/d, escitalopram 20-30 mg/d). We do not typically rely on an arbitrary upper cut-off on the HRSD because an arbitrary cut-off number would not capture the clinical salience of individual symptoms and clinical judgment must supersede (e.g. a HRSD of 18 but in the presence of active suicidal ideation and plan would exclude patient). HDRS-17/Clinician Psychiatric History
5. Individuals who cannot tolerate medications of class and dose at the specified duration defined in inclusion item #4. Psychiatric History
6. Patients currently on medication must be at the same stable dose(s) for 1 month prior to enrollment and be willing to continue at the same dose(s) through the duration of the study. Physician Evaluation
7. Capable and willing to provide informed consent Physician Evaluation
8. Signed HIPAA authorization. Physician Evaluation

9. Willingness to undergo research fMRI scan (3T).
10. Willingness to undergo randomization to either treatment arm.
- 11. Left/Right-handed. Edinburgh Handedness Questionnaire**

Create or insert table to describe the exclusion criteria and methods to ascertain them

1. Investigators, and their immediate families (defined as a spouse, parent, child or sibling, whether by birth or legal adoption). Self Report
2. Individuals diagnosed by the investigators with the following conditions: Bipolar Disorder (lifetime), any Psychotic Disorder (lifetime), history of substance abuse or dependence within the past year (except nicotine and caffeine). Physician Evaluation SCID, DSM-IV
3. Behavior, which in the judgment of the investigator may hinder the patient in completing the procedures required by the study protocol. Physician Evaluation Private Psychiatrist Reports

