4. Individuals with a clinically defined neurological disorder including, but not limited to: tics, space occupying brain lesion; any history of seizures except those therapeutically induced by ECT; history of cerebrovascular accident; history of fainting; transient ischemic attack within two years; cerebral aneurysm, Dementia; Parkinson's Disease; Huntington chorea; Multiple Sclerosis. Physician Evaluation Medical Records
5. Increased risk of seizure for any reason, including prior diagnosis of increased intracranial pressure (such as after large infarctions or trauma), or history of significant head trauma with loss of consciousness for ≥ 5 minutes. Patients Reports
6. Use of any investigational drug within 12 weeks of the randomization visit. Patients Reports
7. Significant acute suicide risk, defined as follow: suicide attempt within the previous 6 months that required medical treatment; or ≥ 2 suicide attempts in the past 12 months; or in the investigator's opinion, has significant risk for suicide based on the current state or recent history. Physician Evaluation
8. Cardiac pacemakers, implanted medication pumps, intracardiac lines, or acute, unstable cardiac disease. Physician Evaluation
9. Intracranial implants (e.g. aneurysms clips, shunts, stimulators, cochlear implants, or electrodes) or any other metal object within or near the head, excluding the mouth, that cannot be safely removed. Physician Evaluation MRI Screening Form
10. Current illicit drug use (cannabinoid, phencyclidine, amphetamines, barbiturates, cocaine, methadone, and opiates), defined as drug use during the 6 months before screening. Physician Evaluation
11. Known or suspected pregnancy. Urine pregnancy test Women who are breast-feeding. Self Report
12. Women of childbearing potential not using a medically accepted form of contraception when engaging in sexual intercourse. Self Report
13. Medicinal patch, unless removed prior to the MR scan. Clinical interview
14. MDD patients with very severe depression, defined as a total HDRS-17 score ≥ 23 , will be excluded and referred to immediate treatment.
15. Risks related to seizures, such as substance abuse or sleep disruptions/insomnia. Clinician Psychiatric History. SCID.
16. History of treatment with rTMS therapy for any disorder. Patients Reports.

Inclusion/Exclusion Criteria #2

Name the subject group/sub sample

Depressed patients non-responders to standard TMS

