Create or insert table to describe the inclusion criteria and methods to ascertain them

Eligibility screening may be conducted under

**WIRB Protocol #20141643, “Cognitive Changes During Treatment with TMS for Major Depression”,
[name], Principal Investigator; or**

**NYSPI IRB Protocol #6669R, “Evaluation of Potential Participants for Depression Evaluation Service
(DES) Research”, [name], Principal Investigator**

If participants were enrolled in either of these studies and the screening evaluations were conducted within the prior six months, copies of all screening instruments will be made and reviewed by the study Principal Investigator. Eligibility would be determined based upon the results of the existing evaluations and the Principal Investigator will document their continued validity.

Inclusion criteria:

1. Male or female outpatients, 18 to 60 years of age. Self report
2. Primary diagnosis of Major Depressive Disorder as confirmed by the Structured Clinical Interview for DSM-IV-TR Disorders (SCID-IV-TR). SCID, DSM-IV-TR
3. Duration of the index episode of at least 2 weeks. Psychiatric History
4. MDD symptoms, defined as a total HDRS-17 score ≥ 18 despite treatment with an adequate trial of a serotonin reuptake inhibitor (SRI). An adequate SRI trial is defined as treatment for at least 6-8 weeks on the SRI, that meets the maximum recommended dosage level for MDD (fluoxetine 40-60 mg/d, sertraline 100- 200 mg/d, paroxetine 40-60 mg/d, fluvoxamine 200-300 mg/d, citalopram 40-60 mg/d, escitalopram 20-30 mg/d). We do not typically rely on an arbitrary upper cut-off on the HRSD because an arbitrary cut-off number would not capture the clinical salience of individual symptoms and clinical judgment must supersede (e.g. a HRSD of 18 but in the presence of active suicidal ideation and plan would exclude patient). HDRS-17/Clinician Psychiatric History
5. Individuals who cannot tolerate medications of class and dose at the specified duration defined in inclusion item #4. Psychiatric History
6. Patients currently on medication must be at the same stable dose(s) for 1 month prior to enrollment and be willing to continue at the same dose(s) through the duration of the study. Physician Evaluation
7. Capable and willing to provide informed consent. Physician Evaluation
8. Signed HIPAA authorization. Physician Evaluation
9. **Left/Right-handed. Edinburgh Handedness Questionnaire**
10. Willingness to undergo research fMRI scan (3T).

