11. Willingness to undergo randomization to either treatment arm.
12. History of NON-response to rTMS in THIS depressive episode. Assessment of history from patient and/or Clinical Psychiatric History from [name] office

Create or insert table to describe the exclusion criteria and methods to ascertain them

1. Investigators, and their immediate families (defined as a spouse, parent, child or sibling, whether by birth or legal adoption). Self Report
2. Individuals diagnosed by the investigators with the following conditions: Bipolar Disorder (lifetime), any Psychotic Disorder (lifetime), history of substance abuse or dependence within the past year (except nicotine and caffeine). Physician Evaluation SCID, DSM-IV-TR
3. Behavior, which in the judgment of the investigator may hinder the patient in completing the procedures required by the study protocol. Physician Evaluation Private Psychiatrist Reports
4. Individuals with a clinically defined neurological disorder including, but not limited to: tics, space occupying brain lesion; any history of seizures except those therapeutically induced by ECT; history of cerebrovascular accident; history of fainting; transient ischemic attack within two years; cerebral aneurysm, Dementia; Parkinson's Disease; Huntington chorea; Multiple Sclerosis. Physician Evaluation Medical Records
5. Increased risk of seizure for any reason, including prior diagnosis of increased intracranial pressure (such as after large infarctions or trauma), or history of significant head trauma with loss of consciousness for ≥ 5 minutes. Patients Reports
6. Use of any investigational drug within 12 weeks of the randomization visit. Patients Reports
7. Significant acute suicide risk, defined as follow: suicide attempt within the previous 6 months that required medical treatment; or ≥ 2 suicide attempts in the past 12 months; or in the investigator's opinion, has significant risk for suicide based on the current state or recent history. Physician Evaluation
8. Cardiac pacemakers, implanted medication pumps, intracardiac lines, or acute, unstable cardiac disease. Physician Evaluation
9. Intracranial implants (e.g. aneurysms clips, shunts, stimulators, cochlear implants, or electrodes) or any other metal object within or near the head, excluding the mouth, that cannot be safely removed. Physician Evaluation MRI Screening Form

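### Group 2 entry can be decided on an HDRS-17 up to six months old that may predate the failed first TMS course, and the protocol does not clearly secure a re-rating

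*Protocol*

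**What the plan says.** **Re-use of screening.** Inclusion/Exclusion Criteria #2 (Group 2) allows eligibility screening under the referring rTMS study or under protocol 6669R. If "the screening evaluations were conducted within the prior six months", the rule is: "Eligibility would be determined based upon the results of the existing evaluations and the Principal Investigator will document their continued validity". Consent Procedures and Study Procedures repeat it.

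**Who enters Group 2.** Recruitment Procedures has patients "selected from those already participating in an approved clinical study of rTMS for treatment resistant depression". Inclusion 12 for Group 2 requires "History of NON-response to rTMS in THIS depressive episode".

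**Severity limits.** Inclusion 4 reads "MDD symptoms, defined as a total HDRS-17 score" of at least 18. Exclusion 14 removes "MDD patients with very severe depression, defined as a total HDRS-17 score" of 23 or more.

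**Length of a course.** Background, Significance and Rationale describes the referring clinics' experience: "of the 139 patients that received 9 weeks of TMS, 60 responded at the 4 week point".

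**Whether assessments are repeated.** Under Study Procedures, the Screening text has patients clinically assessed against every criterion after consent and before enrolment. Assessment Instruments says that SCID and HRSD come from the referring protocol and that this study performs no assessments of its own; it then lists assessments at NYSPI. Consent Procedures answers yes to screening under a different IRB protocol, while Justification for Waiver or Alteration of Consent says screening is done under this one.

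**The concern.** The same re-use rule appears in the criteria for Group 1. There it does little harm, since those patients have had no TMS. Group 2 is defined by a treatment course that may lie between the re-used screening and entry. A severity score from before that course describes the patient before an intervention that may have changed the score without reaching response.

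If the old score decides entry, Group 2 can include patients who do not currently meet the HDRS-17 criterion and can turn away others who do. The randomised sample would then not be the population the criteria describe. An analysis plan cannot repair this afterwards, because it cannot recreate a rating that was never taken.

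**Working it through.** There is no stated figure to reproduce. The checks are on timing, on the score limits, and on the text.

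**1. Can the old score fit the window?** Inputs: six months, about 26 weeks (Group 2 criteria); a 9-week course (Background; assumed to apply to the failed first course).

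26 − 9 = 17 weeks to spare. A rating made before a full first course can be re-used if the second-course decision comes within about 17 weeks of that course ending.

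**2. Can old and current scores disagree?** Inputs: eligible HDRS-17 from 18 to 22 (inclusion 4, exclusion 14); non-response means a fall of less than 50% (Study Procedures). That definition refers to HDRS, or to HDRS-24, while entry uses HDRS-17. The check assumes similar percentage falls on both versions.

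For an old score b, a non-responder ends above b/2. The smallest fall that puts the patient below 18 is (b − 17)/b.

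| Old score b | Lowest score still a non-response | Smallest fall that leaves the range |
|---|---|---|
| 18 | 10 | 1/18 = 5.6% |
| 19 | 10 | 2/19 = 10.5% |
| 20 | 11 | 3/20 = 15.0% |
| 21 | 11 | 4/21 = 19.0% |
| 22 | 12 | 5/22 = 22.7% |

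From any eligible old score, a fall of 22.7% or more but less than 50% is a non-response that takes the current score below the entry limit. Worked example: 22 to 14 is (22 − 14)/22 = 36.4%; the patient qualifies on the old score only. The reverse also occurs: 30 to 20 is (30 − 20)/30 = 33.3%; the patient qualifies on the current score only.

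**3. Does the text prevent this?**

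- The Principal Investigator's note of continued validity is a documentation step. No new rating is required by it.
- The assessment after consent, under Screening, would prevent it if it includes a new HDRS-17.
- Assessment Instruments says the opposite and then lists NYSPI assessments, so it also conflicts with itself.
- Consent Procedures and the waiver justification disagree on which protocol does the screening.

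A site reading these sections cannot tell whether a current HDRS-17 is required.

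**The case against.** The case on the other side is substantial. Screening under other protocols is optional, whereas the assessment after consent is written as something every patient undergoes. Other criteria presuppose current status: medication must have been stable for the month before enrolment, and exclusion 14 sends very severe patients to immediate treatment, which makes little sense for a months-old score. A Principal Investigator who certified a 22 for a patient now at 14 would arguably be breaching the safeguard. The re-use rule names no scale, and the referring protocol's screening schedule is in an attachment that is not shown.

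Much of this stands. The intent was probably to assess patients as they are at entry, and a re-used score predating the failed course is an inference. But intent does not resolve the conflict between Screening and Assessment Instruments, and the re-use rule sits inside the Group 2 criteria as the stated basis for eligibility.

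A reader might go further and infer that second-course response is measured from a score before the first course, so that first-course improvement inflates the response rates. Study Procedures does leave the starting or baseline HDRS without a named time point, and it calls the visit between the cycles the second visit. The text nevertheless favours the second-course start. Group 2 enters after non-response. HDRS-24 is rated weekly in the second course, with a worsening trigger measured from baseline. The timing table and diagram are not shown, and an analysis plan could fix the time point. This is a wording gap and not a demonstrated error.

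**Conclusion.** The point holds for eligibility. The protocol states a rule under which an HDRS-17 that may predate the failed course can decide Group 2 entry, and its safeguards are either not a re-rating or are contradicted elsewhere. It should be corrected; confidence is medium.

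Size: a five-point eligible range, about 17 weeks of slack in the window, and opposite answers for non-responders whose score fell by at least 5.6% to 22.7%, depending on the old score. How many of the 30 planned Group 2 patients would be affected cannot be computed, because the document gives no distribution of score changes and no dates of re-used ratings.

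Assumptions: the first course lasted 9 weeks, the referring study's screening came before it, and HDRS-17 and HDRS-24 fall by similar percentages.

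A reader might also infer that the comparison of targeted with standard TMS is biased. The document does not support that: the entry score is settled before randomisation and the rule is the same for both arms. What is affected is who is in Group 2.

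**What to change.** For Group 2, require an HDRS-17 taken after the failed first course and before randomisation, at the visit already planned right before the second cycle. Use that score for eligibility and do not carry over older symptom scores. Other screening results may still be re-used under the six-month rule.

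Reconcile the Group 2 criteria, Consent Procedures, the waiver justification, the Screening text and Assessment Instruments on where, when and under which protocol eligibility is assessed.

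As a clarification only, state in Study Procedures that the HDRS-24 from that same visit is the baseline for second-course response. If the attached timing table already says so, the body text should match it.

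Inclusion 4 also says "We do not typically rely on an arbitrary upper cut-off on the HRSD", while exclusion 14 sets one. The clinical team must reconcile these; no limit is proposed here.

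Cost: protocol wording and one rating at an existing visit. Some patients who qualify on an old score may not qualify on a current one, which may slow enrolment.
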